ULN	Upper Limit of Normal
WHO-DD	World Health Organization Drug Dictionary
AUC	Area under the concentration time curve
AUC_{∞}	Area under the concentration time curve from time zero to infinity
AUC_{∞}/D	Area under the concentration time curve per dose
AUC_%Extrap	Ratio of area under the concentration-time curve from t_{last} to infinity versus AUC _{∞}
AUCt	at time t
AUC _t /D	AUC _t per dose
AUC _{168h}	Area under the concentration-time curve from time zero to 168 hours
AUC _{168h} /D	AUC _{168h} per dose
CL/F	Apparent clearance of drug from plasma after extravascular administration
CL/F/BW	Apparent clearance of drug from plasma after extravascular administration per body
	weight
C _{max}	Maximum (peak) plasma concentration of the drug
C _{max/D}	C _{max} per dose
LLOQ	Lower limit of quantification
λ_z	Terminal elimination rate constant
$\lambda_{z}(\text{point})$	Number of points used in computing λ_Z
$\lambda_{z}(lower)$	Lower limit on time for values to be included in the calculation of $\lambda_{\rm Z}$
$\lambda_{z}(upper)$	Upper limit on time for values to be included in the calculation of λ_Z

	Goodness of fit statistic for the terminal elimination phase, adjusted for the number of
$\lambda_{z}(RSQ)$	points used in the estimation of λ_Z
t _{1/2,z}	Terminal phase elimination half life
t _{last}	Time of the last measurable concentration
t _{max}	Time to maximum (peak) plasma concentration

1 Introduction

This statistical analysis plan describes the statistical methodology and data analysis algorithms and conventions to be applied for statistical analysis in this trial. This plan is based on version 3.0 of Protocol No. 331-102-00150, dated 28 Jan 2020.

2 Trial Objectives

The objective of the clinical trial is to evaluate the PK, tolerability, and safety of brexpiprazole QW formulation administered as single and repeated administration in patients with schizophrenia.

3 Trial Design

3.1 Type/Design of Trial

This is a multi-center, open-label, clinical pharmacology trial to investigate the PK, tolerability, and safety of brexpiprazole QW formulation administered as single and repeated administration in patients with a diagnosis of schizophrenia (295.90) based on the DSM-5[®]. The trial comprises the single administration period (Cohort 1) and the repeated administration period (Cohort 2). The dose used in the repeated administration period (Cohort 2) will be determined based on plasma drug concentrations obtained in the single administration period (Cohort 1). The single administration period (Cohort 1) comprises Period 1, in which the conventional tablet will be administered, and Periods 2 and 3, in which the QW formulation will be administered. If the single administration period (Cohort 1) fails to produce sufficient plasma drug concentrations, another single administration period (Cohort 1') will be added during which the QW formulation will be administered at higher single doses. Only if progression to the repeated administration period (Cohort 2) is judged to be appropriate based on the results of the single administration period (Cohort 1 and Cohort 1' [as necessary]), will the repeated administration period (Cohort 2) be implemented (see Figure 3.1-1). The repeated administration period (Cohort 2) comprises Period 1, in which subjects will receive a single administration of the conventional tablet, and Period 2, in which subjects will receive 5 administrations of the QW formulation.

In the single administration period (Cohort 1), subjects will receive a brexpiprazole 2 mg conventional tablet on Day 1 of Period 1, the QW formulation at 24 mg on Day 1 of Period 2, and the QW formulation at 48 mg on Day 1 of Period 3, all as single administrations in a fasted state.

In the single administration period (Cohort 1'), subjects will receive a brexpiprazole 2 mg conventional tablet on Day 1 of Period 1, the QW formulation at 30 mg on Day 1 of Period 2, and the QW formulation at 60 or 54 mg on Day 1 of Period 3, all as single administrations in a fasted state.

In the repeated administration period (Cohort 2), subjects will receive a single administration of a brexpiprazole 2 mg conventional tablet on Day 1 of Period 1, and repeated administration of the QW formulation on Days 1, 8, 15, 22, and 29 of Period 2. The doses of the QW formulation will be determined based on the results of the single administration period (Cohort 1 and Cohort 1' [as necessary]).

In the single administration period (Cohort 1 and Cohort 1' [as necessary]), subjects will be required to be hospitalized at the trial site from the day of IMP administration (Day 1) through the eighth day following IMP administration (Day 8) in Period 1 (conventional tablet) and Periods 2 and 3 (QW formulation). For the other parts of the single administration period, they may remain in the trial site or make trial visits on an outpatient basis. In Period 1 (conventional tablet) of the repeated administration period (Cohort 2), subjects will be required to be hospitalized at the trial site from the day of IMP administration (Day 1) through the eighth day following IMP administration (Day 8). For the other parts of Period 1, they may remain in the trial site or make trial visits on an outpatient basis. In Period 2 (QW formulation) of the repeated administration period (Cohort 2), subjects will be required to be hospitalized at the trial site or make trial visits on an outpatient basis. In Period 2 (QW formulation) of the repeated administration period (Cohort 2), subjects will be required to be hospitalized at the trial site from the day of the first IMP administration (Day 1) through Day 16, from Day 22 through Day 23, and from Day 29 through Day 36. For the other parts of Period 2, they may remain in the trial site or make visits on an outpatient basis.

*Whether or not to add Cohort 1', and the doses used in Cohort 1' will be determined based on the results of Cohort 1.

tration Period The doses may be changed depending on the results of the single administration (Cohort 1 and Cohort 1' [as necessary]).					
Period 1	Period 2			Follow-up period	
(20 days)	(42 days)			(Days 56 to 60 of Period 2)	
Single administration of 1 brexpiprazole 2 mg tablet	Repeated ac	lministration Day 1: 24 ys 8, 15, 22, 2	of QW form mg* 29: 48 mg*	ulation]
The administration 20 days (+ 8 days max) Subjects must stay at the trial site from the day of IMP administration (Day 1) through Day 8 in Period 1. For the other parts of the Period 1. subjects may remain in the trial site or make	IMP administration (Day 8) Subjects must stay IMP administration (Day 1) Subjects must stay IMP administration through Day 23, an 2. For the other part the trial site or m	IMP administration (Day 15) y at the trial s h (Day 1) thr d from Day 2 is of the Peric pake trial visi	IMP administration (Day 22) ite from the ough Day 10 29 through D 29 subject ts on an out	A IMP administration (Day 29) day of the first 5, from Day 22 bay 36 in Perio s may remain patient basis.	Postdose follow-up
	Period The doses n (Cohort 1 an Period 1 (20 days) Single administration of 1 brexpiprazole 2 mg tablet Washout period 2 days (+ 8 days max) Subjects must stay at the trial site from the day of IMP administration (Day 1) through Day 8 in Period 1. For the other parts of the Period 1. subjects may remain in the trial site or make trial visits on an outpatient basis.	Period The doses may be changed deperiod (Cohort 1 and Cohort 1' [as necessive period 1 (20 days)) Single administration of 1 brexpiprazole 2 mg tablet Washout period 1 Repeated ad Da IMP administration of 1 brexpiprazole 2 mg tablet IMP administration (Day 1) Washout period 2 days (+ 8 days max) IMP administration (Day 1) Subjects must stay at the trial site from the day of IMP administration (Day 1) through Day 8 in Period 1. For the other parts of the Period 1, subjects may remain in the trial site or make trial visits on an outpatient basis.	Period The doses may be changed depending on the (Cohort 1 and Cohort 1' [as necessary]). Period 1 Period (20 days) (42 day Single administration of 1 brexpiprazole 2 mg tablet Repeated administration Day 1: 24 Days 8, 15, 22, 2 Image: Stable t Image: Stable t Washout period Image: Stable t Washout period Image: Stable t Madministration (Day 1: 24 Days 8, 15, 22, 2 Image: Stable t Mage: Stable t Image: Stable t Madministration (Day 1) thr day of IMP administration (Day 1) thr through Day 23, and from Day 2. For the other parts of the Period 1. For the other parts of the Period 1. Subjects may remain in the trial site or make trial visit on an outpatient basis. Subjects mast stay at the trial site or make trial visit on an outpatient basis.	Period The doses may be changed depending on the results of the (Cohort 1 and Cohort 1' [as necessary]). Period 1 Period 2 (20 days) (42 days) Single administration of 1 brexpiprazole 2 mg tablet Repeated administration of QW form Day 1: 24 mg* Days 8, 15, 22, 29: 48 mg* Image: tablet Image: tablet Image:	Period The doses may be changed depending on the results of the single administration (Cohort 1 and Cohort 1' [as necessary]). Period 1 Period 2 (20 days) (42 days) Single administration of 1 brexpiprazole 2 mg tablet Repeated administration of QW formulation Day 1: 24 mg* Days 8, 15, 22, 29: 48 mg* Image: State of the period 2 of days (+ 8 days max) Image: State of the period 1 ministration (Day 1) Image: Subjects must stay at the trial site from the day of the first form the day of IMP administration (Day 1) through Day 16, from Day 22, subjects may remain in the trial site or make trial visits on an outpatient basis.

*The dose may be changed depending on the results of the single administration period (Cohort 1 and Cohort 1' [as necessary]).

Figure 3.1-1 Trial Design

3.1.1 Cohort 1 (Single Administration Period)

Subjects judged eligible at screening will receive one brexpiprazole 2 mg conventional tablet on Day 1 of Period 1, one 24 mg tablet of the QW formulation on Day 1 of Period 2, and two 24 mg tablets of the QW formulation on Day 1 of Period 3, all as a single oral administration in a fasted state. The trial includes a washout period of 20 days (+ 8 days max) between IMP administration in Period 1 and IMP administration in Period 2 and a washout period of 27 days (+ 8 days max) between IMP administration in Period 2 and IMP administration in Period 3. Brexpiprazole-naïve subjects should be monitored after conventional tablet administration in Period 1 to check if they are free from allergic or hypersensitive reactions. Following administration of the QW formulation in Period 2, safety must be carefully evaluated. Subjects who meet any of the criteria for withdrawal before dose increase as specified in Protocol Section 3.9.3.2 Criteria for Withdrawal Before Dose Increase of the QW Formulation must be withdrawn from the trial and not advance to Period 3. If a subject withdrawn from the trial at the discretion of the sponsor after receiving a brexpiprazole 2 mg conventional tablet in Period 1 and undergoing the examinations scheduled for up to Day 14 of Period 1 subsequently takes part in the trial again, the subject will be allowed to resume participation in the trial from Period 2. If a subject withdrawn from the trial at the discretion of the sponsor after receiving a 24 mg tablet of the QW formulation in Period 2 and undergoing the examinations scheduled for up to Day 14 of Period 2 subsequently takes part in the trial again, the subject will be allowed to resume participation in the trial from Period 3.

3.1.2 Cohort 1' (Additional Single Administration Period, as Necessary)

A simulation of repeated administration will be performed based on the results of Cohort 1 (single administration period). If steady-state plasma brexpiprazole concentrations of the QW formulation are estimated to fall far below the steady-state trough concentration for the 2 mg conventional tablet, Cohort 1' will be added.

The design described in Section 3.1.1 Cohort 1 (Single Administration Period) applies to Cohort 1' as well.

The doses of the QW formulation to be used in Cohort 1' (as necessary) (single administration period) will be determined according to Protocol Section 3.8 Procedure for Progression to the Repeated Administration Period (Cohort 2) From the Single Administration Period (Cohort 1 and Cohort 1' [as Necessary]), and the QW formulation will be administered in a fasted state as per regimen 1 or 2 shown in Table 3.2.1.2.2-1. Brexpiprazole-naïve subjects should be monitored after conventional tablet administration in Period 1 to check if they are free from allergic or hypersensitive

Statistical Analysis Plan

reactions. Following administration of the QW formulation in Period 2, safety must be carefully evaluated. Subjects who meet any of the criteria for withdrawal before dose increase as specified in Protocol Section 3.9.3.2 Criteria for Withdrawal Before Dose Increase of the QW Formulation must be withdrawn from the trial not advance to Period 3.

3.1.3 Cohort 2 (Repeated Administration Period)

Subjects judged eligible at screening will receive a single administration of a brexpiprazole 2 mg conventional tablet on Day 1 of Period 1 in a fasted state. The trial includes a washout period of 20 days (+ 8 days max) between IMP administration in Period 1 and IMP administration in Period 2. Subjects will then receive repeated administration of the QW formulation in a fasted state as per one of the regimens 1 to 5 shown in Table 3.2.1.3.2-1 on Days 1, 8, 15, 22, and 29 of Period 2. Brexpiprazole-naïve subjects should be monitored after conventional tablet administration in Period 1 to check if they are free from allergic or hypersensitive reactions.

3.2 Trial Treatments

3.2.1 Dose, Regimen and Treatment Period

3.2.1.1 Cohort 1 (Single Administration Period)

3.2.1.1.1 Administration of Brexpiprazole Conventional Tablet

On Day 1 of Period 1, subjects will receive a single oral administration of a brexpiprazole 2 mg conventional tablet together with approximately 150 mL of water in the morning after at least 10 hours of fasting. Subjects are not to take any food until 4 hours after administration. Subjects are not to take any fluids from 1 hour before administration of the conventional tablet until 2 hours after administration, except for the water taken at the time of administration.

3.2.1.1.2 Administration of Brexpiprazole QW Formulation

On Day 1 of each of Periods 2 and 3 in Cohort 1 (single administration period), subjects will receive a single oral administration of the QW formulation at the dose specified in Table 3.2.1.1.2-1 together with approximately 150 mL of water in the morning after at least 10 hours of fasting. Subjects are not to take any food until 4 hours after administration. Subjects are not to take any fluids from 1 hour before administration of the QW formulation until 2 hours after administration, except for the water taken at the time of administration.

Table 3.2.1.1.2-1 Doses (Co			ort 1) (Single A	Administra	ation Period)	
	Dose					
Treatment period	Period 2		nt Period 2 Period 3			
Regimen	Dose	Tablet	No. of Tablets	Dose	Tablet	No. of Tablets
1	24 mg	24 mg tablet	1 tablet	48 mg	24 mg tablet	2 tablets

3.2.1.2 Cohort 1' (as Necessary) (Single Administration Period)

3.2.1.2.1 Administration of Brexpiprazole Conventional Tablet

On Day 1 of Period 1, subjects will receive a single oral administration of a brexpiprazole 2 mg conventional tablet together with approximately 150 mL of water in the morning after at least 10 hours of fasting. Subjects are not to take any food until 4 hours after administration. Subjects are not to take any fluids from 1 hour before administration of the conventional tablet until 2 hours after administration, except for the water taken at the time of administration.

3.2.1.2.2 Administration of Brexpiprazole QW Formulation

On Day 1 of each of Periods 2 and 3 in Cohort 1' (as necessary) (single administration period), subjects will receive a single oral administration of the QW formulation together with approximately 150 mL of water in the morning after at least 10 hours of fasting. Subjects are not to take any food until 4 hours after administration. Subjects are not to take any fluids from 1 hour before administration of the QW formulation until 2 hours after administration, except for the water taken at the time of administration. The doses of the QW formulation to be used in Cohort 1' (as necessary) (single administration period) will be determined according to Protocol Section 3.8 Procedure for Progression to the Repeated Administration Period (Cohort 2) From the Single Administration Period (Cohort 1 and Cohort 1' [as Necessary]), and the QW formulation will be administered in a fasted state as per regimen 1 or 2 shown in Table 3.2.1.2.2-1.

Table 3.2.1.2.2-1Doses (Cohort 1' [as Necessary] [Single Administration Period])						
			Do	ose		
Treatment period		Period 2			Period 3	
Regimen	Dose	Tablet	No. of Tablets	Dose	Tablet	No. of Tablets
1	30 mg	30 mg tablet	1 tablet	54 mg	24 mg tablet 30 mg tablet	1 tablet each
2	30 mg	30 mg tablet	1 tablet	60 mg	30 mg tablet	2 tablets

3.2.1.3 Cohort 2 (Repeated Administration Period)

3.2.1.3.1 Administration of Brexpiprazole Conventional Tablet

On Day 1 of Period 1, subjects will receive a single oral administration of a brexpiprazole 2 mg conventional tablet together with approximately 150 mL of water in the morning after at least 10 hours of fasting. Subjects are not to take any food until 4 hours after administration. Subjects are not to take any fluids from 1 hour before administration of the conventional tablet until 2 hours after administration, except for the water taken at the time of administration.

3.2.1.3.2 Administration of Brexpiprazole QW Formulation

In Period 2, subjects will be orally administered the QW formulation together with approximately 150 mL of water in the morning after at least 10 hours of fasting, as per one of regimens 1 to 5 shown in Table 3.2.1.3.2-1 based on the results of the single administration period (Cohort 1 and Cohort 1' [as necessary]). Subjects are not to take any food until 4 hours after administration. Subjects are not to take any fluids from 1 hour before administration of the QW formulation until 2 hours after administration, except for the water taken at the time of administration.

Table 3.2.1.	3.2-1	Doses (Coh	ort 2 [Repeat	ed Admi	inistration Peri	od])		
		Dose						
Treatment period		Period 2						
Day		1 8, 15, 22, and 29			1			129
Regimen	Dose	Tablet	No. of Tablets	Dose	Tablet	No. of Tablets		
1	24 mg	24 mg tablet	1 tablet	48 mg	24 mg tablet	2 tablets		
2	18 mg	18 mg tablet	1 tablet	36 mg	18 mg tablet	2 tablets		
3	24 mg	24 mg tablet	1 tablet	42 mg	18 mg tablet 24 mg tablet	1 tablet each		
4	30 mg	30 mg tablet	1 tablet	54 mg	24 mg tablet 30 mg tablet	1 tablet each		
5	30 mg	30 mg tablet	1 tablet	60 mg	30 mg tablet	2 tablets		

3.3 Trial Population

Patients from 18 years of age to under 65 years of age with a diagnosis of schizophrenia (295.90) based on DSM-5[®]

3.4 Trial Visit Window

Nominal time points will be used for summary of safety parameters and plasma concentration.

4 Sample Size

The target number of subjects is not based on a statistical hypothesis test. A simulation was performed with the PK model created based on PK data on the conventional tablet and QW-A formulation used in the QW-A formulation group in Trial 331-102-00021 conducted in Japan, and the probability that the mean plasma concentration of brexpiprazole after repeated administration of the QW-A formulation would be within the target range of concentration was determined. On the basis of this probability, the sample size was determined to be 20 subjects each for the single administration period (Cohort 1) and the repeated administration period (Cohort 2). Likewise, the sample size for an additional single administration period (Cohort 1') with a new dose was also determined to be 20 subjects.

5 Statistical Analysis Sets

5.1 Pharmacokinetic Analysis Set

The PK analysis set will consist of subjects who received the QW formulation and had plasma drug concentration measurements. The following subjects will be excluded from the PK analysis set:

• Subjects who vomited within 12 hours postdose

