3.7.6.1.2 Brexpiprazole QW Formulation

In Periods 2 and 3 of the single administration period (Cohort 1 and Cohort 1' [as necessary]) and Period 2 of the repeated administration period (Cohort 2), blood samples after dosing of the QW formulation will be collected at the time points shown in Table 3.7-1 and Table 3.7-2 or at withdrawal. Acceptable windows for blood sampling after dosing of the QW formulation are shown in Table 3.7-4 to Table 3.7-6.

[Rationale for time points for blood sampling]

Time points for blood sampling for the conventional tablet were determined based on the following: A single oral dose trial (331-07-002), a multiple oral dose trial (331-10-001), a bioequivalence trial of oral solution (331-10-005), and a bioavailability trial of orally disintegrating tablets (331-102-00019) were conducted in Japan. After conventional tablets 2 mg and 4 mg were administered as a single dose, the median t_{max} for the unchanged drug was 6 hours, and the mean elimination half-life, which was determined at 3 to 8 time points between 36 to 312 hours postdose, was 52.9 to 72.7 hours. A total of 13 time points, namely, predose and 2, 4, 6, 8, 12, 24, 48, 72, 120, 168, 240, and 312 hours postdose, were set for blood sampling in Period 1 of both the single administration period (Cohort 1 and Cohort 1' [as necessary]) and the repeated administration period (Cohort 2) to cover the PK process from absorption to elimination, with reference to the results of the above 4 trials as well as "Partial Amendments to Guideline for Bioequivalence Studies of Generic Products (PFSB/ELD Notification No.0229-10 dated 29 Feb 2012)" (hereinafter referred to as "BE Guideline"), Section 3 Test, A. II. 1. 5) Measurement of biological samples, b. Sampling schedule.

Time points for blood sampling for the QW formulation were determined with reference to the PK data on the OROS formulation from a clinical pharmacology trial (Japan 331-102-00021) for comparative investigation of the PK, tolerability, and safety of 3 types of brexpiprazole QW formulation administered as single oral doses in patients with schizophrenia and with reference to the BE Guideline. A total of 11 time points, namely, predose and 3, 9, 24, 36, 48, 72, 120, 168, 240, and 312 hours postdose, were set for

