3.9.3.3 Documenting Reasons for Discontinuation

All subjects have the right to withdraw and the investigator or subinvestigator can discontinue a subject's participation in the trial at any time if medically necessary. In addition, subjects meeting the following criteria must be withdrawn from the trial. Only one reason for discontinuation (the main reason) can be recorded in the eCRF.

- Adverse event:
 - Continuation of IMP would place the subject at undue risk as determined by the investigator or subinvestigator
 - Safety concern possibly, probably, or likely related to IMP
 - SAE
 - Exacerbation or progression of the underlying disease

- Meeting the criteria for withdrawal before dose increase
- Subject decides to discontinue because of annoyance or discomfort due to a nonserious AE which is not otherwise determined to be an undue hazard
- Subject vomits within 12 hours after IMP administration
- Subject shows allergic reaction or hypersensitivity to brexpiprazole
- Withdrawal of informed consent by the legal representative of the subject
- Withdrawal of informed consent by the subject
- Lost to follow-up
- Pregnancy (see Section 5.5 Pregnancy)
- Investigator's or subinvestigator's decision (other than AE)
- Major protocol deviation
- Termination of all or part of the trial by the sponsor
- Other (record details)

If the subject discontinues IMP due to an AE, the investigator, subinvestigator, or other trial personnel, will make every effort to follow the event until the event is resolved or stabilized, or the subject is lost to follow-up or has died. The procedures in Section 5.7 Follow-up of Adverse Events must be followed.

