10.2 Technical Details of Pharmacokinetic Statistical Analyses

- 1) Using the PK analysis set, the following analysis will be performed.
 - a) For each concentration in Section 10.1.1.1 1), Section 10.1.1.2 1), Section 10.1.1.3 1) and 3), and Section 10.1.2 1)), descriptive statistics will be calculated by cohort, period, and treatment at each blood collection time point. The descriptive statistics to be calculated will be number of analyzed subjects, number of subjects included in the tabulation, arithmetic mean, standard deviation, coefficient of variation, minimum, median, and maximum. However, the descriptive statistics will be calculated only when the number of subjects included in the tabulation exceeds half of the number of analyzed subjects.
 - b) For each parameter in Section 10.1.1.1 2) and 3), Section 10.1.1.2 2), 3), and 4), Section 10.1.1.3 2), and Section 10.1.2 2), descriptive statistics will be calculated by cohort, period, and treatment. For the PK parameters except for t_{max} and t_{last}, the descriptive statistics to be calculated will be number of analyzed subjects, number of subjects included in the tabulation, arithmetic mean, standard deviation, coefficient of variation, geometric mean, minimum, median, and maximum. For t_{max} and t_{last}, descriptive statistics to be calculated will be number of analyzed subjects, minimum, median, and maximum. For t_{max} and t_{last}, descriptive statistics to be calculated will be number of analyzed subjects. For λ_z and λ_z(Rsq), λ_z(point), λ_z(upper) and λ_z(lower), which is outputted as reference values when calculating λ_z, no descriptive statics will be calculated.
- 2) Nonacceptance of data will be determined in accordance with the following conditions in this trial.
 - a) If blood sampling is conducted outside the time window for the analyses (see Table 3.7-3, Table 3.7-4 Table 3.7-5, Table 3.7-6 in the protocol), the data will be excluded from the calculation of descriptive statistics for plasma concentrations at that time point. However, it will be used for the calculation of PK parameters, and if the calculation of PK parameters is determined to be unsuitable, the parameter will not be adopted.
 - b) None of the plasma concentrations after use of drugs or food (see Appendix 3 in the protocol) which may inhibit or induce CYP2D6 or CYP3A4 activity will be used for calculating descriptive statistics at that time.

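### Vomiting within 12 hours of a dose removes the whole subject from the PK analysis set, so valid concentrations collected before the event drop out of every PK summary

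*SAP*

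**What the plan says.** SAP 5.1 defines the set by subject: "The PK analysis set will consist of subjects who received the QW formulation and had plasma drug concentration measurements". It then states "The following subjects will be excluded from the PK analysis set", and the only entry is "Subjects who vomited within 12 hours postdose". Protocol 7.2.1 has the same rule. Neither says which dose or period is meant, or what happens to data collected before the event.

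SAP 10.2 opens its analysis rules with "Using the PK analysis set, the following analysis will be performed". The summaries that follow cover the Period 1 tablet, Periods 2 and 3 of the single-dose cohorts, and the fifth-dose profile and troughs of Cohort 2.

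Protocol 3.9.3.3 makes the same event a reason for mandatory withdrawal: under the statement that "subjects meeting the following criteria must be withdrawn from the trial" it lists "Subject vomits within 12 hours after IMP administration".

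**The concern.** The exclusion works on the subject, while the problem it addresses belongs to one dose. Vomiting may spoil the profile of the dose just taken and, in Cohort 2, the concentrations that build on it. It cannot change a concentration measured earlier. Read as written, a Cohort 1 subject who vomits after the Period 3 dose loses a complete tablet profile and a complete 24 mg profile, and a Cohort 2 subject who vomits after the fifth dose loses the tablet profile and four valid troughs.

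Withdrawal does not explain this. It stops future data and gives no reason to set aside past data. At stake are some precision in the earlier-period and trough summaries, and a PK population selected partly on a tolerability event.

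**Working it through.** The plan's own figure here is 20 subjects per cohort, derived from a simulation whose model, target range and probability are not given. It cannot be reproduced and is not disputed.

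**1. Comparison with the other data rules.**

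| Situation | Rule | Unit removed |
|---|---|---|
| Sample out of window | SAP 10.2, item 2a: "the data will be excluded from the calculation of descriptive statistics for plasma concentrations at that time point"; PK parameters are still calculated unless judged unsuitable | Concentration or parameter |
| Use of a CYP2D6 or CYP3A4 inhibitor or inducer | SAP 10.2, item 2b | Concentrations after use |
| Sample at discontinuation | SAP 10.2, item 4: used if within window | None |
| Withdrawal for another reason after a QW dose | SAP 5.1: still meets the definition | None |
| Vomiting within 12 hours | SAP 5.1 | Whole subject |

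Vomiting is the only one of these that removes the subject.

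**2. Doses for which the rule matters.** A subject who vomits after the Period 1 tablet is withdrawn before any QW dose and never enters the set. The rule therefore bites on QW doses. Because the subject is withdrawn, the valid data at issue all precede the event.

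**3. Valid samples lost per affected subject.** Inputs from Protocol 3.7.6.1.2: Period 1 has 13 samples ("A total of 13 time points"); Period 2 of the single-dose cohorts has 7; Period 3, and the fifth dose of Cohort 2, have 11 each. Table 3.7-2 places a predose sample before each of the five Cohort 2 doses; those before doses 2 to 5 are the 168-hour troughs of doses 1 to 4.

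- Cohort 1, vomiting after the Period 2 dose: 13.
- Cohort 1, vomiting after the Period 3 dose: 13 + 7 = 20, of a possible 13 + 7 + 11 = 31.
- Cohort 2, vomiting after dose k: 13 + k, of which k − 1 are troughs. Dose 1 gives 14 with no trough; dose 5 gives 18 with four troughs.

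The Cohort 1 counts cover complete earlier periods only; the predose sample of the affected dose would add one to each. The Cohort 2 counts already include it.

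**4. Chance that it happens.** With per-subject probability p, P(at least one of 20) = 1 − (1 − p)^20, and the expected number is 20p.

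| Assumed p | P(at least one) | Expected number |
|---|---|---|
| 1% | 0.18 | 0.2 |
| 2% | 0.33 | 0.4 |
| 3/67 = 4.5% | 0.60 | 0.9 |

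The 3/67 is the vomiting count in the 12 mg group of the QT/QTc trial (Protocol 1.2.2.2). It comes from conventional tablets over 11 days of multiple dosing, with no 12-hour limit, so it serves only as an illustrative upper end.

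**5. Precision at stake.** Table 1.2-2 gives Cmax for the QW-A formulation as 61.11 (SD 39.75), so CV = 39.75/61.11 = 65%. The 95% half-width for a mean, relative to the mean, is t(0.975, n − 1) × CV/√n: 30.4% at n = 20 and 29.6% at n = 21. Keeping one additional partial subject in a Period 2 summary gains less than one percentage point. The CV rests on six subjects at 12 mg.

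**The case against.** **The target is protected.** Protocol 3.3.1.1 sets the target as 20 subjects completing the last assessment. A subject withdrawn for vomiting is not a completer. This stands. A reader might infer that each case removes 5% of the planned cohort; that does not follow, because what is lost is partial data from a subject additional to the 20.

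**Exposure bias is not shown.** A reader might infer that the rule pulls summarised exposure downward. That requires vomiting to be related to exposure, which the documents do not establish. The QW-A median tmax in Table 1.2-2 was 30.13 hours (range 23.25 to 49.57), so vomiting within 12 hours precedes that dose's expected peak. Residual drug from earlier Cohort 2 doses could still matter, so an effect is possible, but no size or direction can be given.

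**The dose decision is not shown to be affected.** Protocol 3.8.1 bases the Cohort 2 dose on simulation from Cohort 1 concentrations and does not limit these to the SAP 5.1 set. The excluded subjects are also identified in listing SUBEX-1.

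**Some of the retained data are of limited use.** The tablet serves mainly as a within-subject reference (Protocol 2.3.1), and ratios needing an excluded period would be missing anyway. This is partly right, but SAP 10.1.2 summarises the tablet in its own right, and Period 2 Cmax, relative Cmax and troughs are QW endpoints.

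**Whole-subject exclusion keeps the periods matched.** This fails. Subjects withdrawn for other reasons stay in the set with partial data, so the periods are not matched under the current plan either.

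**Conclusion.** The point stands in a limited form. Following SAP 5.1 and Protocol 7.2.1 as written discards valid pre-event data, and this is out of line with how SAP 10.2 treats other data problems and with the treatment of subjects withdrawn for other reasons.

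The consequence is modest: no planned full profile is lost, and the effect is confined to the Period 1, Period 2 and trough summaries. How often it would arise rests wholly on assumed rates. In particular, the 60% at the upper end of the range should not be read as a forecast for this formulation. It is a cheap improvement and does not threaten the trial's conclusions.

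**What to change.** In SAP 5.1 and Protocol 7.2.1, say which dose the 12 hours are counted from, and replace the subject-level exclusion with a dose-level one, with a matching item in SAP 10.2:

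- exclude concentrations and parameters from the affected dose onward;
- keep earlier periods, earlier troughs and the predose sample of the affected dose;
- set to missing any ratio that needs excluded data.

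The withdrawal rule in Protocol 3.9.3.3 is unchanged.

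The cost is wording in both documents and a record-level flag. No new data are needed, since Protocol 5.1 already records the date and time of onset of vomiting. The small downside is that N will differ between periods; SAP 10.2 already accommodates this by reporting the number analysed separately from the number tabulated. Settling the rule before data lock also avoids a later choice between a subject-level and a dose-level reading.
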